### 6.4 Assessment of Safety

The safety profile of the IMP will be assessed through the recording, reporting and analysis of baseline medical conditions, AEs, physical examination findings including vital signs and eyes signs and symptoms, and laboratory tests.

Comprehensive assessment of any apparent toxicity experienced by each subject will be performed from the time of giving informed consent and throughout the trial. The Investigator will report any AEs, whether observed by the Investigator or reported by the subject (see Section 6.4.1.2). Given the intended MoA, particular attention will be given to AEs that may follow the enhanced T-cell activation such as persistent rash, diarrhea and colitis, autoimmune hepatitis, arthritis, glomerulonephritis, cardiomyopathy, uveitis and other inflammatory eye conditions, or other immune-related reactions. Ophthalmologic examinations should be considered, when clinically indicated, for signs or symptoms of uveitis. Furthermore, due to the anti-TGF $\beta$  activity, particular

attention will also be given to events associated with, anemia, and rash with hyperkeratosis / keratoacanthoma and squamous cell carcinoma of the skin.

The reporting period for AEs is described in Section 6.4.1.3.

The safety assessments will be performed according to the Schedules of Assessments (see **Tables 1-3**).

#### 6.4.1 Adverse Events

#### 6.4.1.1 Adverse Event Definitions

#### Adverse Event

An AE is any untoward medical occurrence in a subject or clinical investigation subject administered a pharmaceutical product, regardless of causal relationship with this treatment. An AE can therefore be any unfavorable and unintended sign (including an abnormal laboratory finding), symptom, or disease temporally associated with the use of a medicinal product, whether or not considered related to the medicinal product.

For surgical or diagnostic procedures, the condition / illness leading to such a procedure is considered as the AE rather than the procedure itself.

In case of a fatality, the cause of death is considered as an AE, and the death is considered as its OUTCOME.

The investigator (or physician designee) is responsible for verifying and providing source documentation, grading the severity and assigning the attribution for all adverse events.

Investigators will reference the NCI-CTCAE v4.03 (publication date: 17 November 2017), a descriptive terminology that can be used for AE reporting.

A general grading (severity / intensity; hereafter referred to as severity) scale is provided at the beginning of the above referenced document, and specific event Grades are also provided.

If a particular AE's severity is not specifically graded by the guidance document, the Investigator is to use the general NCI-CTCAE definitions of Grade 1 through Grade 5 following his or her best medical judgment.

Grade 1:	Mild
Grade 2:	Moderate
Grade 3:	Severe
Grade 4:	Life-threatening
Grade 5:	Death

Recommended Adverse Event Recording Guidelines					
Attribution	Grade 1	Grade 2	Grade 3	Grade 4	Grade 5
Unrelated	Phase I	Phase I	Phase I	Phase I	Phase I
			Phase II	Phase II	Phase II
				Phase III	Phase III
Unlikely	Phase I	Phase I	Phase I	Phase I	Phase I
			Phase II	Phase II	Phase II
				Phase III	Phase III
Possible	Phase I	Phase I	Phase I	Phase I	Phase I
	Phase II	Phase II	Phase II	Phase II	Phase II
		Phase III	Phase III	Phase III	Phase III
Probable	Phase I	Phase I	Phase I	Phase I	Phase I
	Phase II	Phase II	Phase II	Phase II	Phase II
		Phase III	Phase III	Phase III	Phase III
Definitive	Phase I	Phase I	Phase I	Phase I	Phase I
	Phase II	Phase II	Phase II	Phase II	Phase II
	1 11050 11	Phase III	Phase III	Phase III	Phase III

Any clinical AE with severity of Grade 4 or 5 must also be reported as an SAE as per Section 6.4.1.4; however, a laboratory abnormality of Grade 4, such as anemia or neutropenia, is considered serious only if the condition meets one of the serious criteria described below.

If death occurs, the primary cause of death or event leading to death should be recorded and reported as an SAE. "Fatal" will be recorded as the outcome of this specific event and death will not be recorded as separate event. Only, if no cause of death can be reported (for example, sudden death, unexplained death), the death per se might then be reported as an SAE.

Investigators must also systematically assess the causal relationship of AEs to the IMP using the following definitions. Decisive factors for the assessment of causal relationship of an AE to the

M7824 include, but may not be limited to, temporal relationship between the AE and the M7824, the known safety profile of M7824, medical history, concomitant medication, course of the underlying disease, trial procedures.

**Unrelated**: Not reasonably related to the IMP. The AE could not medically (pharmacologically / clinically) be attributed to the IMP under study in this clinical trial protocol. A reasonable alternative explanation must be available.

**Related**: Reasonably related to the IMP. The AE could medically (pharmacologically / clinically) be attributed to the IMP under study in this clinical trial protocol.

#### Abnormal Laboratory Findings and Other Abnormal Investigational Findings

Abnormal laboratory findings and other abnormal investigational findings (for example, on an EKG trace) should not be reported as AEs unless they are associated with clinical signs and symptoms, lead to treatment discontinuation or are considered otherwise medically important by the Investigator. If a laboratory abnormality fulfills these criteria, the identified medical condition (for example, anemia, increased ALT) must be reported as the AE rather than the abnormal value itself.

## 6.4.1.1.1 Serious Adverse Event (SAE) Reporting

An adverse event or suspected adverse reaction is considered "serious" if, in the view of either the investigator or Merck/EMD Serono, it results in any of the following outcomes:

• Death

• A life-threatening adverse drug experience – any adverse experience that places the patient, in the view of the initial reporter, at immediate risk of death from the adverse experience as it occurred. It does not include an adverse experience that, had it occurred in a more severe form, might have caused death.

• Inpatient hospitalization or prolongation of existing hospitalization

• A persistent or significant incapacity or substantial disruption of the ability to conduct normal life functions.

• A congenital anomaly/birth defect.

Important medical events that may not result in death, be life-threatening, or require hospitalization may be considered a serious adverse drug experience when, based upon appropriate medical judgment, they may jeopardize the patient or subject and may require medical or surgical intervention to prevent one of the outcomes listed in this definition. Examples of such medical events include allergic bronchospasm requiring intensive treatment in an emergency room or at home, blood dyscrasias or convulsions that do not result in inpatient hospitalization, or the development of drug dependency or drug abuse (21 CFR 312.32).

• Important medical events as defined above, may also be considered serious adverse events. Any important medical event can and should be reported as an SAE if deemed appropriate by the Principal Investigator or the IND Office.

• All events occurring during the conduct of a protocol and meeting the definition of a SAE must be reported to the IRB in accordance with the timeframes and procedures outlined in "The University of Texas M. D. Anderson Cancer Center Institutional Review Board Policy for Investigators on Reporting Serious Unanticipated Adverse Events for Drugs and Devices". Unless stated otherwise in the protocol, all SAEs, expected or unexpected, must be reported to the IND Office, regardless of attribution (within 5 working days of knowledge of the event).

• All life-threatening or fatal events, that are unexpected, and related to the study drug, must have a written report submitted within 24 hours (next working day) of knowledge of the event to the Safety Project Manager in the IND Office.

• Unless otherwise noted, the electronic SAE application (eSAE) will be utilized for safety reporting to the IND Office and MDACC IRB.

• Serious adverse events will be captured from the time of the first protocol-specific intervention, until 90 days after the last dose of drug, unless the participant withdraws consent. Serious adverse events must be followed until clinical recovery is complete and laboratory tests have returned to baseline, progression of the event has stabilized, or there has been acceptable resolution of the event.

• Additionally, any serious adverse events that occur after the 90 day time period that are related to the study treatment must be reported to the IND Office. This may include the development of a secondary malignancy.

#### **Reporting to FDA**:

• Serious adverse events will be forwarded to FDA by the IND Office (Safety Project Manager IND Office) according to 21 CFR 312.32.

It is the responsibility of the PI and the research team to ensure serious adverse events are reported according to the Code of Federal Regulations, Good Clinical Practices, the protocol guidelines, Merck/EMD Serono's guidelines, and Institutional Review Board policy.

## 6.4.1.1.2 Events Not to Be Considered as AEs / SAEs

Medical conditions present at the initial trial visit that do not worsen in severity or frequency during the trial are defined as Baseline Medical Conditions, and are not to be considered AEs.

#### AE / SAEs Observed in Association with Disease Progression

Progression of the disease / disorder being studied assessed by measurement of lesions on radiographs or other methods as well as associated clinical signs or symptoms (including laboratory abnormalities) should not be reported as an AE / SAE, unless the subject's general condition is more severe than expected and / or unless the outcome is fatal within the AE reporting period (as defined in Section 6.4.1.3).

# 6.4.1.1.3 Pre-defined AEs of Special Interest (AESI) for Safety Monitoring

Any AE that is suspicious to be a potential irAE (see Section 5.5.3.3), including ophthalmologic findings, has to be reported in an expeditious manner and will be considered an AE of special interest (AESI).

Infusion-related reactions / hypersensitivity, regardless of grade, must be reported as AESIs.

In addition, rash with hyperkeratosis / keratoacanthoma / squamous cell cancer of the skin are regarded as AESIs. Please note that squamous cell cancer of the skin should be considered as medically important condition and thus as a serious AESI, which has to be reported in an expedited manner as a SAE.

Anemia when considered related to M7824 will be reported as AESI regardless of grade.

The reporting of AESI is defined in Section 6.4.1.4.

## 6.4.1.2 Methods of Recording and Assessing Adverse Events

At each trial visit, the subject will be queried on changes in his or her condition. During the reporting period, any unfavorable changes in the subject's condition will be recorded as AEs, whether reported by the subject or observed by the Investigator.

Complete, accurate and consistent data on all AEs experienced for the duration of the reporting period (defined below) will be reported on an ongoing basis in the appropriate section of the eCRF (Prometheus). All SAEs and all non-serious AEs of special interest must be additionally documented and reported using the eSAE database.

It is important that each AE report include a description of the event, its duration (onset and resolution dates and times to be completed when it is important to assess the time of AE onset relative to the recorded treatment administration time), its severity, its causal relationship with the trial treatment, any other potential causal factors, any treatment given or other action taken, including dose modification or discontinuation of the IMP, and its outcome. In addition, serious cases should be identified and the appropriate seriousness criteria documented.

### 6.4.1.2.1 Investigator Communications with Merck/EMD Serono

• In addition to the regular reporting obligations, the following reportable events must be submitted to EMD Serono within 48 hours for fatal/life-threatening SAEs and 5 business days for all other SAEs.

• Exposure during pregnancy or breastfeeding (even if not associated with an adverse event) and occupational exposure (even if not associated with an adverse event) shall also be reported.

Contact information for submission of reportable events and monthly extracts to EMD Serono:

E-mail: [contact] or [contact]

#### Specifying:

- PROTOCOL Number
- SUBJECT Number
- SITE Number/PI Name
- SAE/ONSET DATE

#### 6.4.1.3 Definition of the Adverse Event Reporting Period

The AE reporting period for safety surveillance from the first protocol intervention to 90 days after last study drug administration and continues through the trial's 28-Day Safety Follow-up visit, defined as 28 days ( $\pm$  5 days) after last trial drug administration. After the 28-Day Safety Followup visit only AEs that are deemed attributable to trial drug by the Investigator should be documented until the Safety Follow-up visit, defined as 28 days (+/- 7 days) after the last trial drug administration.

Any SAE assessed as related to M7824 must be reported whenever it occurs, irrespective of the time elapsed since the last administration of M7824.

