## 6.4.1.5 Monitoring of Subjects with Adverse Events

Adverse events are recorded and assessed continuously throughout the trial (see Section 6.4.1.3) and are assessed for final outcome at the End of Treatment visit. After the End of Treatment visit only AEs that are deemed attributable to trial drug by the Investigator should be documented until the Safety Follow-up visit.

All SAEs ongoing at the 28-Day Safety Follow-up visit must be monitored and followed up by the Investigator until stabilization or until the outcome is known, unless the subject is documented as "lost to follow-up". In addition, all trial drug related SAEs occurring after 28-Day Safety Follow-up visit and ongoing at the Safety Follow-up visit must be followed up in the same manner.

Reasonable attempts to obtain this information must be made and documented. It is also the responsibility of the Investigator to ensure that any necessary additional therapeutic measures and follow-up procedures are performed.

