## 7.5.3.3 Adverse Events

Severity of AEs will be graded using the NCI-CTCAE v4.03 toxicity grading scale. Safety will be assessed by descriptive statistics and summarized in tabular format. This data will be separated based on organ class, immune-relation, severity and relation to M7824.

Adverse events (serious and non-serious) will be considered treatment emergent adverse events when emerging in the on-treatment period defined as the time from the first trial drug administration to the last drug administration date + 30 days or the earliest date of subsequent anticancer drug therapy minus 1 day, whichever occurs first, unless otherwise stated. All premature terminations will be summarized by primary reason for treatment withdrawal.

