#### Table 10: Toxicity stopping boundaries for Cohort B

The operating characteristics for toxicity monitoring in cohort B are illustrated in Table 11.

True toxicity rate	Prob (stop early)	Average Sample Size
0.10	0.25	28.5
0.20	0.238	24.9
0.30	0.623	18.4
0.40	0.900	12.3
0.50	0.989	8.7

Table 11: Operating Characteristics for Toxicity Monitoring in Cohort B

The stopping boundaries and the operating characteristics for cohorts A-C and B were generated using Shiny application for Bayesian toxicity monitoring (http://qctrlshiny/postprobtoxicity).

AEs of 3 or greater and deemed related to M7824 (section 6.4.1.1.1) will count towards toxicity calculations with respect to interim safety monitoring. AEs of 3 or greater deemed unrelated to M7824 are not included towards safety decision making. These include AEs attributable to disease progression (section 6.4.1.1.2) and abnormal laboratory or investigational values that are asymptomatic or do not result in treatment discontinuation (section 6.4.1.1.1).

The time period that grade 3 AEs attributable to M7824 are counted towards interim safety monitoring decisions is defined from their onset to 90 days after the last dose of study drug (section 6.4.1.1.3).

Any grade 5 event on-study will require suspension of the study pending review of the safety data regarding the death.

The Investigator is responsible for completing an efficacy/safety summary report, and submitting it to the IND Office Medical Affairs and Safety Group, for review and approval. This should be submitted after the first 5 evaluable patients per cohort, complete 1 cycle of study treatment, and every 5 evaluable patients per cohort, thereafter. On every report submission, the information from previous reported patients will need to be updated.

A copy of the cohort summary should be placed in the Investigator's Regulatory Binder under "IND Office correspondence".

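### Section 7.6 counts related Grade 3+ AEs to 90 days after the last dose, but the collection rules conflict on whether the non-serious ones are recorded beyond about day 28

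*Combined protocol and SAP*

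**What the plan says.** **What the rule counts.** Section 7.6 counts "AEs of 3 or greater and deemed related to M7824", without limiting this to serious events. The period over which they are "counted towards interim safety monitoring decisions is defined from their onset to 90 days after the last dose of study drug". For that window it cites section 6.4.1.1.3, which defines AEs of special interest (AESIs) and gives no window.

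**What is to be recorded.**
- Section 6.4.1.3 begins: "The AE reporting period for safety surveillance from the first protocol intervention to 90 days after last study drug administration". The same sentence goes on "and continues through the trial's 28-Day Safety Follow-up visit", at day 28 (± 5). The next sentence says that after that visit only related AEs "should be documented until the Safety Follow-up visit, defined as 28 days (+/- 7 days) after the last trial drug administration". The two visits are in effect the same one.
- Section 6.4.1.5 says of the time from End of Treatment onward: "only AEs that are deemed attributable to trial drug by the Investigator should be documented until the Safety Follow-up visit". Footnote q of Table 1 and footnote r of Tables 2 and 3 say the same.
- Tables 1 to 3 nevertheless mark AE documentation in the 3-monthly long-term follow-up column. Tables 1 and 2 also mark toxicity assessment there.
- Section 6.4.1.1.1 captures SAEs to 90 days after the last dose, and section 6.4.1.3 puts no time limit on related SAEs.

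**The concern.** A stopping rule needs the same window for counting and for recording. Here the counting window is clear and the recording window is not. A site that follows section 6.4.1.5 stops recording related non-serious events at about day 28. A site that follows the opening clause of section 6.4.1.3 goes on to day 90. Between day 28-35 and day 90 lie 55 to 62 days (90 − 35 and 90 − 28) in which an event can count in the rule and yet need not be recorded.

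Late events are meant to reach the rule. Section 5.5.3 warns that immune-related events may appear only after several weeks of treatment, and section 7.6 requires each safety report to update the patients already reported. The operating characteristics in Tables 9 and 11 take the stated toxicity rate as the rate that is observed. If some countable toxicities are never recorded, the rule stops less often than those tables say.

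**Working it through.** **Step 1: follow one event through the text.** Take a non-serious, related, Grade 3 clinical event with onset 60 days after the last dose.

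| Provision | Outcome |
|---|---|
| 7.6, counting window | Counts |
| 6.4.1.3, opening clause | Recorded |
| 6.4.1.3, second sentence | Not required (limit is day 21 to 35) |
| 6.4.1.5 and footnotes q / r | Not required |
| Tables 1-3, long-term AE mark | Recorded if asked about at that contact |
| 6.1.4.2, description of quarterly contact | Survival and further therapy; event follow-up is described for SAEs only |
| 6.4.1.1.1, SAE window | Does not apply |
| 6.4.1.4, AESI route | Applies only if the event is an AESI; no end date given |

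The provisions disagree, and the cross-reference in 7.6 does not settle the matter.

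**Step 2: reproduce the plan's figures.** Inputs from section 7.6: prior Beta(0.4, 1.6); stop if P(p > 0.20 | data) exceeds 0.75 (Cohorts A-C and D) or 0.85 (Cohort B). After x toxicities in n patients the posterior is Beta(0.4 + x, 1.6 + n − x).

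- Cohorts A-C and D: P(p > 0.20) is 0.778 at 2/5, 0.895 at 4/10 and 0.856 at 5/15. One toxicity fewer gives 0.424, 0.720 and 0.687. The boundaries of Table 8 follow.
- Cohort B at 0.85: the boundaries are 3/5, 4/10, 5/15, 7/20, 8/25 and 9/29, as in Table 10.

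Probability of stopping early at a true rate of 0.30, Cohorts A-C and D:

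- Look at 5: P(X ≥ 2) = 1 − 0.7⁵ − 5(0.3)(0.7⁴) = 1 − 0.1681 − 0.3602 = 0.4718.
- Look at 10: P(X₁ = 0)·P(X₂ ≥ 4) + P(X₁ = 1)·P(X₂ ≥ 3) = 0.1681 × 0.0308 + 0.3602 × 0.1631 = 0.0639.
- Sum: 0.536. Table 9 prints 0.532.

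A crossing at the final look is not counted as early; counting it gives 0.632, which does not match. Over all rates, Table 9 is reproduced to within 0.005. The same recursion for Cohort B gives 0.626 at 0.30 (Table 11 prints 0.623) and agrees to within 0.003 in every row but one. At a true rate of 0.10, Table 11 prints 0.25 where the recursion gives 0.025; the printed average sample size of 28.5 agrees with 0.025. That is a separate slip.

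**Step 3: illustrate the loss.** Let m be the share of patients with a countable toxicity whose only qualifying event is not recorded. The rule then sees p(1 − m). The documents give no value for m; 5% and 10% are assumptions.

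| True rate | m | Rate seen | P(stop early), A-C and D | P(stop early), B |
|---|---|---|---|---|
| 0.30 | 0 | 0.300 | 0.536 | 0.626 |
| 0.30 | 5% | 0.285 | 0.499 | 0.569 |
| 0.30 | 10% | 0.270 | 0.462 | 0.509 |
| 0.40 | 0 | 0.400 | 0.752 | 0.900 |
| 0.40 | 5% | 0.380 | 0.714 | 0.863 |
| 0.40 | 10% | 0.360 | 0.673 | 0.817 |

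With m = 0, that is with full recording to day 90, the calculation returns the printed tables, apart from the slip noted above.

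**The case against.** The strongest reply is that most of the relevant data are collected. On-treatment events are recorded. Section 6.4.1.1 requires clinical Grade 4 and 5 events to be reported as SAEs, and SAEs are captured to day 90. What is left is in practice non-serious, clinical, related Grade 3 events that begin after about day 28-35 off drug. The rule counts patients, so such an event matters only if it is the patient's first qualifying toxicity. This stands, and it argues for a small m.

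A reader might infer that the rule runs on data the plan does not collect. The documents do not support that: section 6.4.1.3 opens with 90 days for AEs in general, and the long-term columns mark AE documentation. The text conflicts; it does not clearly omit.

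A reader might also point to laboratory or endocrine events as typical losses. Both are weak examples. Section 7.6 leaves out laboratory values that are asymptomatic or do not lead to discontinuation. A suspected immune-related endocrine event is an AESI, and a non-serious Grade 3 or higher AESI goes into the eSAE database within 5 days. That route has no end date of its own, however, and section 6.4.1.2 ties AE recording to the reporting period that is in dispute, so it narrows the gap without surely closing it.

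Finally, sections 7.5.3.1 and 7.5.3.3 end the treatment-emergent period at "the last drug administration date + 30 days" or at new therapy. A reader might take this as an error that makes the tables understate toxicity. It is a summary definition, it does not feed the stopping rule, and section 7.5.1 lists all recorded data. A tabulation window may differ from a monitoring window.

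**Conclusion.** Wrong as written: sections 6.4.1.3, 6.4.1.5, the schedule footnotes and the schedule tables give conflicting answers on whether a non-serious related Grade 3 or higher clinical event is recorded between about day 28-35 and day 90, although section 7.6 counts it. Confidence in the contradiction is high, because it rests on the text alone.

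The size of the effect is unknown. The 5-10% range has no source in the documents. The calculation also removes the same share at every look. At early looks, which start once five evaluable patients have completed one cycle, many patients are still on drug, and their post-treatment events have not yet happened under any collection rule. The figures therefore show the direction and rough scale of a possible loss of sensitivity; they are not an estimate of it.

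**What to change.** - Rewrite section 6.4.1.3 with one end date, and bring section 6.4.1.5, footnote q of Table 1 and footnote r of Tables 2 and 3 into line, so that all related Grade 3 or higher AEs, serious or not, are documented over the window that section 7.6 counts (90 days as written).
- Say in section 6.1.4.2 that the quarterly contact asks about such events. The first contact falls about three months after the day-28 visit, near day 118 (28 + 90), so one retrospective question covers the whole window.
- Correct the reference in section 7.6 to 6.4.1.1.3; the reporting period is defined in section 6.4.1.3.
- Optional: a display of related events to day 90 beside the day-30 treatment-emergent tables.

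The cost is protocol wording and one added question at a contact that already exists. Boundaries, sample sizes and analyses do not change.
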